
1. Incidence rate will be calculated for each exposure group as follows:
 $\text{Incidence Rate} = \frac{\sum \text{at risk subjects with at least one event}}{\sum \text{subject years at risk}} \times 100$ 
 
- Incidence rate is defined as the number of 'at-risk' subjects experiencing first event (i.e. number of new cases) during the specified follow-up period divided by total subject-years at-risk of that event for all subjects at risk.
 
- Although the categorization of study follow-up time to Benlysta (Exposed) or Non-Benlysta (Unexposed) depends on the exposure assignment strategy (see Appendix 2, Section 9.2.1 for further discussion), the follow-up time included in the subject-years at-risk calculation, for each month xx time period, starts from enrollment date and ends at the earliest of the following: 
 
o First event date
 
o Last contact date (as defined in Section 9.5.3)
 
o Month xx target date (Section 5.3)
 
o Censored date (for While on Initial Exposure strategy; see Section 9.2.1.1)
 
o Data cut-off date
 
 
Additionally, for some exposure strategies (e.g. 'As-Exposed' strategy; see Appendix 2, Section 9.2.1.2), time to treatment switch and risk windows are also considered when categorizing follow-up time into 'Exposed' and 'Unexposed' period.
 
 
- Calculation of an individual's subject-years at-risk for each exposure strategy is shown in Section 9.2.
 
- Subject-years at-risk will be calculated for each event type separately.
 
- Only the first experience of the event (i.e. new cases) or first primary diagnosis (in the case of a malignant event) which occurred during the 'at-risk' period are counted (see Section 9.2.1 for time period considered for each exposure strategy).
 
- For summary of each specific AESI category, subjects experiencing events in multiple AESI categories will be counted in more than 1 AESI category.
 
 
2. Event rate will be computed for each exposure group as follows:
 $\text{Event rate} = \frac{\sum \text{all AESI events}}{\sum \text{subject years of follow-up}} \times 100$ 
 
- Event rate is estimated for potentially recurrent events and represents the average number of events per unit time of follow-up. It is defined as the total number of events experienced by all subjects during the specified study period divided by subject-years of follow-up. The categorization of study follow-up time depends on the exposure strategy (see Appendix 2, Section 9.2.1). The subject-years of follow-up for each month xx time period takes the same definition above for the subject-years at-risk, however, follow-up does not stop at the time of first event.
 
- Additionally, for some exposure strategies (e.g. 'As-Exposed' strategy), time to treatment switch and risk windows are also considered when categorizing follow-up time into exposed and unexposed period (Section 9.2.1.2)
 
- All events experienced during the follow-up period including recurrent events are counted (see Section 9.2.1 for time period considered for each exposure strategy).
 

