## NOTE:

- i. Individual's subject-years at-risk will be calculated for each event type separately and if required for each time period (i.e. for analysis by time period)
- ii. Individual subject-years of follow-up may be required for each time period (i.e. for analysis by time period)

\* Last Contact Date as defined in section 9.5.3

2. While On Initial Exposure analysis approach will be used to analyze all data accrued up to the first treatment switch. Any events and follow-up time accrued after the first exposure switching (switching from Initial Exposure) will be censored (i.e. excluded from analysis) at first exposure switch date (see Section 5.14 for the definition of exposure/medication switching).

A limitation of this analysis approach is potential bias introduced by underreporting of events experienced during the study since data from only a subset of the study period and events collected before the first treatment switch are included in the analysis. The results only present risk of exposure prior to first treatment switch. See Section 9.2.1.2 for details of 'As-Exposed' (Time Varying) approach to address this.

**Programming Hints for derivation of essential variables needed for computation of incidence and events rates (presented in Section 7.1.5.1) under the While On Initial Exposure approach:**

- Compute First Switch Date as:  

$$\text{Baseline Benlysta Medication End Date} + 98 \text{ days (for switching from Benlysta to Non-Benlysta) or}$$

$$\text{First Post-Baseline Benlysta Start Date} - 1 \text{ (for switching from Non-Benlysta to Benlysta)}$$
- Compute individual's subject-years at-risk as:  

$$[(\text{minimum (Event Date, First Switch Date, Last Contact Date}^*) - \text{Study Enrollment Date}) + 1] / 365.25$$

- Compute individual's subject-years of follow-up as:
 
$$\frac{[(\text{minimum}(\text{First Switch Date}, \text{Last Contact Date}^*) - \text{Study Enrollment Date}) + 1]}{365.25}$$
- Consider events experienced up to First Switch Date (if switching from Initial Exposure) or whole study period (if no switch):
 
$$\text{Study Enrollment Date} \leq \text{Event Date} \leq \text{minimum}(\text{First Switch date}-1, \text{Last Contact Date}^*)$$
  - For incidence rate calculation only count new cases (i.e. first onset) of the event experienced during the period
  - For events rate calculation count all the events experienced during the period

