$$\text{Unexposed subject-years} = (\text{Last contact date}^* - \text{Enrollment Date} + 1) / 365.25.$$
  - c) Subjects not on Benlysta at enrollment who do switch on to Benlysta:
 
$$\text{Unexposed subject-years} = (\text{Benlysta start date} - \text{Enrollment date}) / 365.25$$

$$\text{Exposed subject-years} = (\text{Last contact date}^* - \text{Benlysta start date} + 1) / 365.25$$
- For other xx-Month time periods (xx = 12, 24, 36, 48), calculate period follow-up years as follows:

- a) Subjects on Benlysta at enrollment:  
 Exposed period follow-up years =  $(xx\text{-Month period end date} - \text{Enrollment Date} + 1) / 365.25$ .  
 where  $xx\text{-Month period end date}$  = earliest of  $xx\text{-Month target visit date}$  and  $\text{Last contact date}^*$
- b) Subjects not on Benlysta at enrollment who do not switch on to Benlysta before  $xx\text{-Month target visit date}$ :  
 Unexposed period follow-up years =  $(xx\text{-Month period end data} - \text{Enrollment Date} + 1) / 365.25$ .  
 where  $xx\text{-Month period end data}$  = earliest of  $xx\text{-Month target visit date}$  and  $\text{Last contact date}^*$
- c) Subjects not on Benlysta at enrollment who do switch on to Benlysta before  $xx\text{-Month target visit date}$ :  
 Unexposed period follow-up years =  $(\text{Benlysta start date} - \text{Enrollment date}) / 365.25$   
 Exposed period follow-up years =  $(xx\text{-Month period end date} - \text{Benlysta start date} + 1) / 365.25$   
 where  $xx\text{-Month period end data}$  = earliest of  $xx\text{-Month target visit date}$  and  $\text{Last contact date}^*$
- An individual's subject-years 'at-risk' will be calculated for each exposure group as follows:
 

a) Subjects on Benlysta at enrollment:  
 Exposed subject-years at-risk =  $[(\text{minimum}(\text{Event Date}, \text{Last Contact Date}^*) - \text{Study Enrollment Date}) + 1] / 365.25$

b) Subjects not on Benlysta at enrollment who do not switch on to Benlysta before  $xx\text{-Month target visit date}$ :  
 Unexposed subject-years at-risk =  $[(\text{minimum}(\text{Event Date}, \text{Last Contact Date}^*) - \text{Study Enrollment Date}) + 1] / 365.25$

c) Subjects not on Benlysta at enrollment who do switch on to Benlysta before  $xx\text{-Month target visit date}$ :
 
    - i) If no event happens in period:  
 Unexposed subject-years at-risk =  $(\text{Benlysta start date} - \text{Enrollment Date}) / 365.25$ .  

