 Exposed subject-years at-risk =  $(\text{Last contact date}^* - \text{Benlysta start date} + 1) / 365.25$
    - ii) If event happens in period:

Unexposed subject-years at-risk = (minimum (Event date, Benlysta start date) - Enrollment Date)/365.25

Exposed subject-years at-risk =

If Event date  $\geq$  Benlysta start date: (Event date – Benlysta start date+1) /365.25

[figure not shown]
If Event date < Benlysta start date: 0

**NOTE:** An individual's subject-years at-risk will be calculated for each event category separately

\* Last Contact Date as defined in Section 9.5.3

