24.122	Evaluable	Overall Proportion and Rates of Adverse Events of Special Interest [While On Initial Exposure Strategy] – Treatment Initiators	
24.210	Evaluable	Rates of Adverse Events of Special Interest by Time Period [As-Exposed – Time Varying Strategy with 14 Weeks Risk Window]	
24.211	Evaluable	Rates of Adverse Events of Special Interest by Time Period [As-Exposed – Time Varying Strategy with 14 Weeks Risk Window] – Current Users	
24.212	Evaluable	Rates of Adverse Events of Special Interest by Time Period [As-Exposed – Time Varying Strategy with 14 Weeks Risk Window] – Treatment Initiators	
24.310	Evaluable	Rates of Mortality, Serious Infections, Opportunistic Infections, Other Infections of Interest and Serious Psychiatric Events by Time Period [As-Exposed - Time Varying Strategy with 6 Months Risk Window]	
24.311	Evaluable	Rates of Mortality, Serious Infections, Opportunistic Infections, Other Infections of Interest and Serious Psychiatric Events by Time Period [As-Exposed – Time Varying Strategy with 6 Months Risk Window] – Current Users	

Safety Endpoints Tables			
Table No	Analysis Population	Title	Programming Note
24.312	Evaluable	Rates of Mortality, Serious Infections, Opportunistic Infections, Other Infections of Interest and Serious Psychiatric Events by Time Period [As-Exposed – Time Varying Strategy with 6 Months Risk Window] – Treatment Initiators	
24.410	Evaluable	Rates of Mortality, NMSC and Malignancies by Time Period [Ever-Exposed Strategy]	
24.411	Evaluable	Rates of Mortality, NMSC and Malignancies by Time Period [Ever-Exposed Strategy] – Current Users	
24.412	Evaluable	Rates of mortality, NMSC and Malignancies by Time Period [Ever-Exposed Strategy] – Treatment Initiators	

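### The Ever-Exposed at-risk formulas omit the month-xx cut that SAP 7.1.5.1 requires; coded literally, they would distort the exploratory 12- to 48-month incidence rates in Tables 24.410-24.412.

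*SAP*

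**What the plan says.** SAP 9.2.1.3 gives programming hints for the Ever-Exposed strategy and refers to 7.1.5.1 for the rates themselves. It deals with two denominators.

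- **Follow-up years (event rate).** There is a separate set of formulas for the time points: "For other xx-Month time periods (xx = 12, 24, 36, 48), calculate period follow-up years as follows". Each ends at an xx-Month period end date, defined as the earlier of the xx-Month target visit date and the last contact date.
- **Years at risk (incidence rate).** There is one set only: "An individual's subject-years 'at-risk' will be calculated for each exposure group as follows". Cases (a) and (b) end at the earlier of event date and last contact date. Exposed time in (c)(i) ends at last contact, and in (c)(ii) at the event. No formula contains the xx-Month date. Yet case (b) is labelled "Subjects not on Benlysta at enrollment who do not switch on to Benlysta before" the xx-Month target visit date, and (c) is its counterpart for those who do switch before that date.

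The closing note of the section reads "An individual's subject-years at-risk will be calculated for each event category separately" and is silent on time periods. The ITT formulas in 9.2.1.1 are also written without a cut, but their note adds "if required for each time period (i.e. for analysis by time period". The As-Exposed block in 9.2.1.2 has explicit xx-Month at-risk terms.

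The general definition in 7.1.5.1 says that "the follow-up time included in the subject-years at-risk calculation, for each month xx time period, starts from enrollment date and ends at the earliest" of a list of dates, one of which is the Month xx target date. The displays concerned are Tables 24.410 to 24.412, titled "Rates of Mortality, NMSC and Malignancies by Time Period [Ever-Exposed Strategy" in the list in 9.11.2.

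**The concern.** Most of the surrounding text points to a cut: the labels of (b) and (c), the follow-up formulas directly above, and the general definition. The formulas lack it. A programmer working from the hints could put all at-risk time up to last contact under a 12-month count of first events.

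The study tests no hypothesis (SAP 2.4), so the absolute rates and their pattern over time are the result. Ever-Exposed carries out the protocol's once-exposed-always-at-risk rule for NMSC and other malignancies, and is one of the rules for mortality (protocol 8.3.2). A constant hazard that appears to climb from the 12-month column to the overall column could be mistaken for a delayed effect.

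There is also an attribution problem. Read literally, (b) treats a comparison subject who starts BENLYSTA after month xx as a non-switcher and counts at-risk time to last contact as unexposed. The opening of 9.2.1.3 assigns all time after the first BENLYSTA dose to BENLYSTA.

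**Working it through.** **Inputs.** 2,000 and 1,000 patients, 5 years of follow-up, 10% annual drop-out, no crossover, and 7,773 and 3,886 planned patient-years (protocol synopsis and 8.2). Reference rates are 0.68 per 100 patient-years for death and 0.226 for each malignancy endpoint (protocol Table 8-1).

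**Step 1: reproduce the plan's figure.** With exponential drop-out, person-years per subject to year T are PY(T) = (1 - 0.9^T) / (-ln 0.9). PY(5) = 0.40951 / 0.10536 = 3.887. Multiplied by 2,000 and 1,000 this gives 7,773.5 and 3,886.8, which matches.

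**Step 2: cut and uncut denominators.** The cut denominator for month xx is PY(T). The literal one is PY(5). With events cut at month xx, the reported rate is the correct rate times PY(T)/PY(5).

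| Month | PY(T) per subject | BENLYSTA cohort, cut (2,000 × PY(T)) | Uncut/cut | Rate as share of correct | 0.68 would show as | 0.226 would show as |
|---|---|---|---|---|---|---|
| 12 | 0.949 | 1,898 | 4.10 | 24% | 0.17 | 0.055 |
| 24 | 1.803 | 3,607 | 2.16 | 46% | 0.32 | 0.105 |
| 36 | 2.572 | 5,144 | 1.51 | 66% | 0.45 | 0.150 |
| 48 | 3.264 | 6,528 | 1.19 | 84% | 0.57 | 0.190 |

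**Step 3: sensitivity to drop-out.** With none, the shares are T/5: 20%, 40%, 60% and 80%. At an assumed 20% a year, the uncut/cut ratios are 3.36, 1.87, 1.38 and 1.14, so the shares are about 30%, 54%, 73% and 88%. With no drop-out and everyone followed to 63 months, the 12-month ratio is 5.25.

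**Step 4: first-event truncation and crossover.** A simulation of 600,000 subjects, split 2:1 with 10% drop-out, stopped time at the first event and let comparison subjects start BENLYSTA at assumed rates of 0 to 20% a year, applying (b) literally. The 12-month ratio was 4.0 to 4.2 for exposed and 3.7 to 4.1 for unexposed time. The ratio of the two groups' rates changes by the unexposed ratio over the exposed ratio. For the 0.68 rate at 10% crossover this is 3.88/4.11 = 0.94 at 12 months and 2.02/2.19 = 0.92 at 24 months. At 20% it is 3.70/4.18 = 0.89 and 1.89/2.22 = 0.85.

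**Step 5: case (b) for one subject.** A comparison subject starts BENLYSTA at month 18 and is followed event-free to month 60. In the 12-month table the correct contribution is 1.0 unexposed year. Case (b) as written gives 5.0, of which (60 - 18)/12 = 3.5 years follow the first BENLYSTA dose.

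**Step 6: the numerator.** The Ever-Exposed event-mapping line also lacks a month-xx cut. The cut comes from 5.3, which slots events by target study day, and from 7.1.5.1, which counts first events in the specified period. If neither numerator nor denominator is cut, the columns roughly repeat the overall rate and Step 2 does not apply.

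**The case against.** The strongest reply is that the correct rule is already in the SAP. Section 7.1.5.1 is the definition, covers every strategy, and ends at-risk time at the Month xx target date; 9.2.1.3 only offers hints for computing it. A programmer who takes the numerator cut from 7.1.5.1 finds the denominator cut in the same item. This stands in part. It makes the defect a conflict between a general definition and a formula, and the understatement conditional on how the code is written. It does not remove the conflict, because no text says which prevails.

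The opening of 9.2.1.3 also answers the literal reading of (b), since it ends the unexposed period the day before BENLYSTA starts. That too leaves the formula at odds with its own section.

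Third, 7.1.5.1 requires both at-risk and follow-up totals to be shown. At-risk years about four times the follow-up years for the same time point are impossible, so a careful check of the output would catch the error. That is a safeguard, not a specification.

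A reader might infer that early incidence rates will be reported at a quarter of their true value, or that the main safety comparison is compromised. The documents support neither. The first needs the particular combination of cut events and uncut time. On the second, SAP 5.1 makes Ever-Exposed exploratory, and the primary ITT and While On Initial Exposure analyses, their weighted versions, the event rates and the overall rates do not use these formulas.

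**Conclusion.** The internal inconsistency is real and should be corrected. The Ever-Exposed at-risk formulas are wrong for the 12- to 48-month columns of Tables 24.410 to 24.412 and conflict with 7.1.5.1.

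The size depends on the coding. With events cut and time uncut, incidence rates would be about 24%, 46%, 66% and 84% of the correct value, assuming exponential drop-out at the protocol's 10%. A fourfold understatement is not a ceiling (fivefold at 12 months with no drop-out) and is not typical of the later columns (about 1.2-fold at 48 months). With both uncut, the time-period columns would carry almost no time-period information.

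Comparisons between groups at one time point move much less than the absolute rates: by up to about 15% under the crossover rates assumed above, which the documents do not give.

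**What to change.** Leave the current formulas in place for the overall rate. Replacing last contact date throughout would leave that rate without a formula, because the xx-Month period end date is defined only for months 12 to 48. For those months, add to 9.2.1.3:

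- **(a) and (b):** include the xx-Month period end date in the minimum with event date and last contact date.
- **(c)(i):** end exposed time at the xx-Month period end date instead of last contact date.
- **(c)(ii):** apply only if the event falls on or before that date; otherwise treat the subject as (c)(i). Exposed time here runs to the event, so a change to last contact date alone would not cut it.
- **Unexposed time in (c):** keep the existing day count. It has no added day, so moving its end to the day before BENLYSTA starts would lose one day per switcher.
- **Numerator:** count only events on or before the xx-Month period end date.
- **Precedence:** state that 7.1.5.1 governs where the hints differ.

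Program one time point independently against 7.1.5.1, and confirm that at-risk years never exceed follow-up years. The cost is a short SAP correction and a change to the derivation code; no new data are needed.

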### 9.2.2. Exposure Strategy Hypothetical Illustration

The exposure status strategies described in Section 9.2.1 are illustrated in the chart below showing treatment profile of six hypothetical subjects.

[figure not shown]
NOTE: The risk windows are only applicable when switching from Benlysta medication to Non-Benlysta Standard of Care (SOC) medication(s). There are two possible risk windows: (1) 14 weeks (98 days) which assumes that Benlysta exposure ends 14 weeks (98 days) after cessation (End Date) of Benlysta medication; and (2) 6 months.

The events and exposure time contributed by each subject to the two exposure status cohorts (Benlysta or Non-Benlysta) depend on the analysis strategy as shown in the Table below.

Exposure Strategy	Highlights	Exposure Time/Events Attribution per risk windows*	
		BENLYSTA	NON-BENLYSTA

Initial Exposure:
 
 
- Intent-To-Treat (ITT)
 
- While On-Initial Exposure
 
	
ITT
 
 
• Assign exposure status based on baseline (enrollment) SLE medication
 
• Include all events and exposure time during FU irrespective of switching
 
 
While On-Initial Exposure
 
 
• Assign exposure status based on baseline (enrollment) SLE medication
 
• Censor (exclude) events and exposure time post switching
 
	
D – A (subjects 1, 3, 6)
 
D – A (subject 1) B2 – A (subjects 3 & 6)
	
d – a (subjects 2, 4, 5)
 
d – a (subject 2) b - a (subjects 4 & 5)

As-Exposed (Time varying)
	
 
• Allows subjects to switch treatment exposure status based on treatment use
 
• Assign time varying treatment exposure group
 
• Subjects treatment exposure group change over follow-up time depending on switch on and off Benlysta medication
 
• Treatment exposure status is assigned at event and visit data level
 
• Used all data since no censoring of events or follow-up exposure time after switching
 
• Subjects can contribute person-year exposure time to any of treatment exposure groups
 
	
D – A (subject 1) B2 – A & D – C (subject 3) c2 – b (subject 4) d - b (subject 5) B2 – A (subject 6)
	
d – a (subject 2) C – B2 (subject 3) b – a & d – c2 (subject 4) b – a (subject 5) D – B2 (subject 6)


Ever-Exposed
	
 
• Assigns exposure status based on ever being exposed to Benlysta
 
• Considers whether subject was exposed to Benlysta at any point during the follow up period
 
• When subject has not been exposed to Benlysta at any point in time, the subject is considered as 'Unexposed'. Once a subject is exposed to Benlysta even once, they will be considered as always exposed
 
• Treatment exposure status is assigned at event and visit data level
 
• Uses all data
 
• Subjects who start as 'Unexposed' can contribute person-year exposure time to both of the treatment exposure groups if they start taking Benlysta
 
	
D – A (subject 1) D – A (subject 3) d – b (subject 4) d – b (subject 5) D – A (subject 6)
	
d – a (subject 2) b – a (subject 4) b – a (subject 5)

\* Assume at-risk window is only applicable after switching from Benlysta

The same chart could be used to illustrate how events are considered to compute incidence rate. Let's note e1 and e2, two events of same AESI occurring for a subject.

- For initial exposure (i.e. ITT and while on initial exposure), events only contribute to the subject's initial exposure assignment, and only the first event will be considered for the incidence rate computation:
  - Subjects 1, 3 and 6: one event for Benlysta group (e1-A)
  - Subjects 2, 4 and 5: one event for Non-Benlysta group (e1-a)
- For the 'As-Exposed' and 'Ever-Exposed' strategies, subjects can contribute subject-years and events to either one or both exposure groups. The following events will be considered for the incidence rate computation:
  - For subjects 1 and 2, there is no medication (exposure) switching, therefore computation remains as per initial exposure.
  - For subject 3, only the first event is considered for Benlysta group and therefore computation remains as per initial exposure.
  - Subject 4:

- For the as-exposed strategy, one event for Non-Benlysta group (e1-a) and one event for Benlysta group (e2-b) as the event occurred during risk-window of Benlysta period.
- The same applies for the ever-exposed strategy, as subject was not on Benlysta at enrollment and switch on to Benlysta.
- Subject 5:
  - For the as-exposed strategy, one event for Non-Benlysta group (e1-a) and one event for Benlysta group (e2-b).
  - The same applies for the ever-exposed strategy, as subject was not on Benlysta at enrollment and switch on to Benlysta.
- Subject 6:
  - For the as-exposed strategy, one event for Benlysta group (e1-a) and one event for Non-Benlysta group (e2-B2).
  - For the ever-exposed strategy, one event for Benlysta group (e1-A) and none for non-Benlysta group. The subject was on Benlysta at enrollment and is always considered as exposed, therefore computation remains as per initial exposure.

